### Medical and surgical history

Medical and surgical history will be summarized by primary SOC and PT in overall group. The table will be sorted by SOC internationally agreed order and decreasing frequency of PT based on the overall incidence in the overall treatment group. No specific description of the safety parameters will be provided at baseline. If relevant, the baseline values will be described along with each safety analysis.

No specific description of the efficacy parameters will be provided at baseline. If relevant, the baseline values will be described along with each efficacy analysis.

#### **2.4.2 Prior or concomitant medications**

The prior and concomitant medications will be presented for the full analysis population.

Medications will be summarized in overall group according to the WHO-DD dictionary, considering the first digit of the anatomic category (ATC) class (anatomic category) and the first 3 digits of the ATC class (therapeutic category). All ATC codes corresponding to a medication will be summarized, and patients will be counted once in each ATC category (anatomic or therapeutic) linked to the medication. Therefore patients may be counted several times for the same medication.

The table for prior medications will be sorted by decreasing frequency of ATC followed by all other therapeutic classes based on the overall incidence. In case of equal frequency regarding ATCs (anatomic or therapeutic categories), alphabetical order will be used.

The tables for concomitant medications will be sorted by decreasing frequency of ATC followed by all other therapeutic classes based on the overall group. In case of equal frequency regarding ATCs (anatomic or therapeutic categories), alphabetical order will be used.

#### **2.4.3 Extent of investigational medicinal product exposure and compliance**

The extent of eliglustat exposure and compliance will be assessed and summarized for the safety population ([Section 2.3.2](#)).

##### ***2.4.3.1 Extent of investigational medicinal product exposure***

The extent of eliglustat exposure will be assessed by the duration of eliglustat exposure over the course of the study.

Duration of eliglustat exposure is defined as last dose date – first dose date + 1 day, regardless of unplanned intermittent discontinuations (see [Section 2.5.3](#) for calculation in case of missing or incomplete data).

Duration of eliglustat exposure will be summarized descriptively as a quantitative variable (number, mean, SD, median, minimum, and maximum). In addition, duration of treatment exposure will also be summarized categorically by numbers and percentages for each of the

following categories and cumulatively according to these categories:  $\leq 1$  year, 1 to  $\leq 2$  years, 2 to  $\leq 3$  years, 3 to  $\leq 4$  years, 4 to  $\leq 5$  years, and  $>5$  years.

Additionally, the cumulative duration of eliglustat treatment exposure will be provided, defined as the sum of the duration of treatment exposure for all patients, and will be expressed in patient years. A listing of exposure will be produced.

#### **2.4.3.2 Compliance**

A given administration will be considered noncompliant if the patient did not take the planned dose of treatment as required by the protocol over the course of the study period. No imputation will be made for patients with missing or incomplete data.

**Percentage of compliance** for a patient will be defined as the number of capsules taken from Day 1 to end of treatment divided by the total number of capsules that the patient should have taken from Day 1 to end of treatment as per the protocol (BID = 2 capsules per day, QD = 1 capsule per day).

**Above-planned dosing percentage** for a patient is defined as the number of administrations that the patient took more than 105% of planned dose during the on-treatment period.

**Under-planned dosing percentage** for a patient is defined as the number of administrations that the patient took less than 90% of planned dose during the on-treatment period. Treatment compliance, above-planned, and under-planned dosing percentages will be summarized descriptively as quantitative variables (number, mean, SD, median, minimum, and maximum).

The overall compliance will be summarized in categories (<80%, 80% - 90%, 90% - 105%, >105%). In addition, numbers and percentages of patients with at least 1 above-planned dose administration will also be provided, as well as numbers and percentages of patients with 0, (0, 20%], and >20% under-planned dose administrations.

Cases of overdose (defined as actual IMP dose administration is greater than planned dose administration per day) will constitute by protocol as an adverse event of special interest and will be listed as such. More generally, dosing irregularities will be listed in [Section 2.2.1](#).

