10.5.1.3 Adverse event of special interest

An adverse event of special interest (AESI) is an AE (serious or non-serious) of scientific and medical concern specific to Genzyme product or program, for which ongoing monitoring and immediate notification by the Investigator to Genzyme is required. Such events may require further investigation in order to characterize and understand them. Adverse events of special interest may be added or removed during a study by protocol amendment.

For this study the following AEs will be considered as AESI and should be reported as such to GPE:

- Clinically significant cardiac arrhythmias detected by ECG or Holter monitoring that do not meet criteria for an SAE.
- Syncope from any cause.
- Pregnancy of a female patient as well as pregnancy occurring in a female partner of a male patient.
- Pregnancy will be qualified as an SAE only if it fulfills one of the seriousness criteria (see Section 10.5.1.2).

In the event of pregnancy in a female patient, IMP should be suspended. See [Section 10.4.3](#) for detail.

Female patients will be instructed to notify the investigator immediately if they discover they are pregnant. Pregnant female patients will be discontinued from the study.

Male patients will be instructed to notify the investigator immediately if they discover that their sexual partner is pregnant.

If the investigator learns of a report of pregnancy at any time after signing the informed consent, the investigator should follow the instructions in [Section 10.5.4](#) to contact the sponsor within 24 hours; however, the investigator will be asked to complete the Pregnancy forms rather than SAE forms. The patient will be followed until the outcome of the pregnancy is known (eg, live birth or stillbirth). The investigator will be responsible for this follow-up.

Follow-up of the pregnancy in a female patient or in a female partner of a male patient is mandatory until the pregnancy outcome has been determined, unless prohibited by local regulations.

- Symptomatic overdose (serious or non-serious) with IMP
 - A symptomatic overdose (accidental or intentional) with the IMP is an event suspected by the Investigator or spontaneously notified by the patient (not based on systematic pills count) and defined as administration of a quantity of IMP per administration or per day, which is above the maximum recommended dose according to the authorized product information

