If overdose is suspected, the patient will be asked to suspend the IMP immediately and come back to the site for appropriate monitoring.

Asymptomatic overdose has to be reported as a standard AE.

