11.4.1 Extent of study treatment exposure and compliance

The extent of study treatment exposure and compliance will be assessed and summarized by actual treatment received within the safety population.

Duration of IMP exposure is defined as: last dose date – first dose date + 1 day, regardless of unplanned intermittent discontinuations.

A given period of administration will be considered noncompliant if the patient takes less than 90% or more than 105% of the planned dose of treatment as required by the protocol. No imputation will be made for patients with missing or incomplete data. Treatment compliance, above-planned and under-planned dosing percentages will be summarized descriptively (N, Mean, SD, Median, Min, and Max). The percentage of patients with compliance categorized as <80%, 80%-90%, 90%-105%, >105% will be summarized.

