### ***2.1.4.1 Adverse events variables***

#### ***Adverse event observation period***

- Pre-treatment adverse events are adverse events that developed or worsened or became serious during the pre-treatment period.
- Treatment-emergent adverse events (TEAEs) are adverse events that developed or worsened or became serious during the treatment-emergent period (treatment-emergent adverse event observation period).
- Post-treatment adverse events are adverse events that developed or worsened or became serious during the post-treatment period.

Continuous monitoring will be performed for (S)AEs and concomitant medications. Results of pregnancy testing for female patients of childbearing potential will be collected. Patients with an SAE or AESI should be followed until event resolution or when follow-up is no longer considered medically necessary, or the patient is lost to follow-up.

All adverse events (including SAEs and AESIs) will be will be coded to a lower-level term (LLT), preferred term (PT), high-level term (HLT), high-level group term (HLGT), and associated primary system organ class (SOC) using the version of Medical Dictionary for Regulatory Activities (MedDRA) currently in effect at Sanofi at the time of database lock.

Adverse events (including serious adverse events and adverse event of special interest) will be recorded from the time of signed informed consent until the end of the study.

Any SAE (including death) brought to the attention of the Investigator at any time after the end of the study for the patient and considered by him/her to be caused by the IMP with a reasonable possibility, should be reported to Global Pharmacovigilance department and will not be recorded in the clinical database.

Serious adverse events and adverse events of special interest (AESI) are defined in the protocol (refer to protocol Section 10.5.1.2 and 10.5.1.3). AESI will be identified and summarized based on CRF information, not standardized or customized MedDRA queries.

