### **2.2.1 Randomization and drug dispensing irregularities**

Since the study is an open-label follow-up study and IVRS was not implemented, the randomization and drug dispensing irregularities is not applicable.

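### SAP 2.4.3.2 credits the protocol with an overdose AESI rule that the protocol does not contain, and it leaves two dosing percentages without a denominator or a workable unit

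*SAP*

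**What the plan says.** **Overdose.** SAP 2.4.3.2 refers to "Cases of overdose (defined as actual IMP dose administration is greater than planned dose administration per day" and states that these cases "will constitute by protocol as an adverse event of special interest and will be listed as such". It sets no condition on symptoms. Other dosing irregularities are sent to SAP 2.2.1, which says that "the randomization and drug dispensing irregularities is not applicable".

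Protocol 10.5.1.3 names symptomatic overdose as the AESI. The quantity taken must be one "which is above the maximum recommended dose according to the authorized product information", and the event must be suspected by the investigator or volunteered by the patient; systematic pill counts are expressly excluded as a basis. It then adds: "Asymptomatic overdose has to be reported as a standard AE". SAP 2.1.4.1 points to this protocol section for the AESI definition and says that "AESI will be identified and summarized based on CRF information, not standardized or customized MedDRA queries".

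**Dosing percentages.** In SAP 2.4.3.2 the above-planned dosing percentage "is defined as the number of administrations that the patient took more than 105% of planned dose during the on-treatment period". The under-planned percentage is worded the same way with a 90% limit. Both are summarised as quantitative variables, and under-planned dosing is also banded as 0, (0, 20%] and >20%. The overall percentage of compliance, in the same section, is a true ratio: capsules taken over capsules due.

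**Unit for the limits.** Protocol 11.4.1 reads: "A given period of administration will be considered noncompliant if the patient takes less than 90% or more than 105% of the planned dose".

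**The concern.** The overdose sentence cites the protocol as its authority, and the protocol says something narrower. It is not a declared change: SAP 1.5 reports no modification to the protocol's statistical section, and SAP 1.6 mentions only the treatment-emergent period. AESIs need notification within 24 hours, while ordinary AEs are reported routinely (Protocol 10.5.4, Table 2). A listing built on the SAP sentence would therefore show AESIs with no matching expedited report, and it would disagree with the AESI tables and listing in SAP 2.4.5.1. AESIs are among the key safety results for the two-year report (SAP Section 3).

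For the dosing percentages, a programmer cannot produce the 20% bands from the definitions given without choosing a denominator that the SAP does not state. The 90% and 105% limits also need a unit on which they can discriminate.

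**Working it through.** The documents give no figure on this point to reproduce. The overdose question is a comparison of texts; the percentages need only short arithmetic.

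**1. Overdose rules side by side**

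| Element | SAP 2.4.3.2 | Protocol 10.5.1.3 |
|---|---|---|
| Threshold | planned daily dose | maximum recommended dose in the product information |
| Symptoms | not required | required for AESI status |
| Identification | not stated | investigator or patient, not systematic pill count |
| Asymptomatic case | AESI | ordinary AE |

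The two thresholds need not coincide, because Protocol 8.1.1 allows the planned dose to be reduced for certain concomitant medicines. The product information is not in the documents, so the gap cannot be sized.

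**2. What one extra capsule does**

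Inputs: 728 days to Week 104 (SAP Table 2), with 2 capsules per day for BID and 1 for QD (SAP 2.4.3.2).

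- Planned capsules: BID 728 × 2 = 1456; QD 728 × 1 = 728.
- Compliance with one extra capsule: BID 1457/1456 = 100.07%; QD 729/728 = 100.14%.
- Extra capsules needed to pass 105%: more than 0.05 × 1456 = 72.8 (BID) or 0.05 × 728 = 36.4 (QD).

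So a patient well inside the 90%-105% category would still appear as an AESI under the SAP sentence.

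**3. Count against percentage**

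Formula: percentage = 100 × count / planned administrations. This denominator is an illustrative choice, since the SAP gives none.

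- Ten missed administrations: BID 1000/1456 = 0.69%; QD 1000/728 = 1.37%. As written, both patients score 10.
- The >20% band begins above 0.20 × 1456 = 291.2 missed administrations (BID) or 0.20 × 728 = 145.6 (QD).

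The same count thus stands for percentages that differ two-fold between regimens, and a pooled mean of counts would mix the two.

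**4. Unit for the 90% and 105% limits**

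One planned administration is one capsule (Protocol 8.1). The ratio of taken to planned can then be only 0%, 100%, 200% and so on. Any limit between 0% and 100%, or between 100% and 200%, would give the same classification, so 90% and 105% do no work at that level.

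**5. Whether a visit interval would serve as the period**

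Protocol 11.4.1 does not define its period. Assume one period per 6-month visit interval, since unused treatment is returned at each visit (Protocol 8.4.1).

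- Two years: 4 periods. One under-dosed period is 1/4 = 25%, already >20%, so (0, 20%] cannot be reached.
- The band first becomes reachable with 5 periods (1/5 = 20%).

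Moving to the period without defining it would therefore break the band table at the main analysis.

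**The case against.** The strongest reply is that little is affected. SAP 2.1.4.1 takes the AESI definition from the protocol and identifies AESIs from the CRF, so the AESI overview, incidence tables and listing in SAP 2.4.5.1 follow the right rule. The overall compliance ratio and its four categories are sound, and the count of patients with at least one above-planned administration needs no denominator. All of this stands.

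It can also be said that a variable called a percentage and cut at 20% is plainly meant as a proportion. That is fair. A reader might infer that the raw count will be compared with 20 and that well-compliant patients will land in the top band. The text requires that only if the percent sign is ignored, and the overall compliance table would still show such patients correctly. What remains is that the denominator is missing.

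The SAP does not define an administration, so its wording may be shorthand for the protocol's period. That makes the unit an ambiguity rather than a proven change of method, but the two texts still need the same term.

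Finally, SAP 2.2 already tabulates critical or major deviations, including drug-dispensing irregularities, and the not-applicable note in 2.2.1 is explained by the open-label design without an interactive response system. This makes the cross-reference a small slip. Above-plan dosing that is not a critical or major deviation is still left without a stated output.

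**Conclusion.** The point holds in limited form. The overdose sentence in SAP 2.4.3.2 misstates the protocol and contradicts SAP 2.1.4.1. Two dosing percentages lack a denominator, and the unit for the 90% and 105% limits does not match Protocol 11.4.1. The affected outputs are the overdose/AESI listing under 2.4.3.2, the summaries of the two dosing percentages and the under-planned band table.

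A reader might go further and infer that the AESI tables or the compliance results as a whole are wrong. The documents do not support that, because those outputs rest on the CRF and on a proper ratio. Nor is there an effect on efficacy: the FAS requires only one dose, SAP Appendix B lists no subgroup analysis for the efficacy endpoints, and all analyses are descriptive.

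I put no number of patients on the mislabelled overdoses, because the documents give no rate of extra capsules. Assumed independent daily chances from 0.0001 to 0.005, with 32 patients followed for 728 days, give about 2 to 31 patients with at least one such day, by 32 × [1 − (1 − p)^728]. That range is too wide to be informative.

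The arithmetic on percentages assumes one capsule per administration and an unchanged regimen over 728 days. The empty-band result assumes that a period equals a 6-month visit interval.

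**What to change.** In SAP 2.4.3.2:

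- **(a) Overdose.** Reconcile the sentence with Protocol 10.5.1.3, so that only events recorded as AESIs on the CRF are listed as AESIs. List other above-plan dosing as dosing irregularities in 2.4.3.2 itself, and remove the reference to Section 2.2.1.
- **(b) Percentages.** Define each as 100 × count / number of planned units for that patient, with the same unit above and below the line. Planned dosing days or planned administrations would keep the 20% cut usable at two years.
- **(c) Limits.** Reconcile the unit for the 90% and 105% limits with Protocol 11.4.1 and define the period of administration. If it is to be the 6-month visit interval, the under-planned bands need to change as well.

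The cost is SAP wording and minor programming, best done before the two-year database lock. Parts (a) and (b) need no new data if planned dosing days or administrations are used and intake is recorded at that level. The CRF is not in the documents, so that should be confirmed when the unit is chosen.

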#### **2.4.4 Analyses of efficacy endpoints**

In reference to the study period, efficacy result will be evaluated for all patients at the 2 year point by measured values (eg, category of bone pain, or bone density value in g/cm^2) and changes from baseline (eg, shift in category of bone pain or absolute and percent change from baseline in BMD g/cm^2 or incidence over 2 years, as appropriate).

In reference to the period of eliglustat treatment, efficacy result will be evaluated 2 years after study entry, but results will be grouped by duration of eliglustat treatment at the time of analysis. The actual groupings will depend on the distribution of treatment duration at the time of analysis (eg,  $\leq 5$  years versus  $>5$  years).

When the study has completed, summaries will be performed comparing to the 2 baselines as described above if applicable.

All efficacy endpoints will be summarized descriptively; no hypothesis testing will be performed. In general, descriptive statistics (number, mean, standard deviation, minimum and maximum) of the absolute value, change from baseline and/or percentage change from baseline for continuous endpoints will be analyzed. Summary statistics (count, percentage) will be summarized for the categorical endpoints. Cumulative incidence (n, percentage), incidence rate (n/year), or other descriptive statistics will also be displayed as appropriate. Calculations and summaries will include all non-missing data at a given time point, imputation will not be performed.

By-patient data listings containing efficacy endpoints will be produced if necessary.

All the below mentioned other efficacy endpoint analyses will be produced for the full analysis population. Refer to [Section 2.5.3](#) for details on handling dropouts, missing data, and patients who have more than one value assessed within the same time frame.

#### **2.4.4.1 Analysis of primary efficacy endpoint(s)**

The main efficacy endpoints of interest are five common manifestations of Gaucher's disease summarized separately which includes:

- Mobility, bone pain and bone crisis, as assessed by the Gaucher Disease clinical assessments;
- Bone marrow infiltration;
- BMD;
- Lytic lesions, osteonecrosis, fractures and infarcts;
- Bone biomarkers.

##### **2.4.4.1.1 Mobility, bone pain and bone crisis**

Category of mobility status and bone pain, as well as number of new bone crises, will be summarized by visit. Absolute value, change from baseline and percent change from baseline of bone crisis over time will be summarized using descriptive statistics by visit using two baselines (study baseline and eliglustat baseline). Additionally, shifts in category of mobility and pain from study and eliglustat baseline by each post-baseline visit will be presented.

##### **2.4.4.1.2 Bone marrow infiltration**

Bone marrow infiltration score by location and total bone marrow infiltration score will be summarized both continuously and categorically. Absolute values, change and percent change from baseline (study baseline and eliglustat baseline) will be summarized by visit. Category of total infiltration score (Mild: 0 to 4; Moderate: 5 to 8; Severe: 9-16) will be constructed and summarized by visit. Shifts in category of infiltration from study and eliglustat baseline will be summarized by each post-baseline visit.

#### **2.4.4.1.3 BMD**

Absolute value, change and percent change from baseline (study baseline and eliglustat baseline) for bone mineral density in (g/cm^2), T and Z scores by location will be summarized by visit. Shift in bone density categories of T and Z scores will be summarized by visit. In addition, mean plots of absolute values and percent change from baseline for total BMD, T-scores, and Z-scores for all patients with standard deviation will be provided.

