11.4.2 Analyses of efficacy endpoints

11.4.2.1 Analysis of primary efficacy endpoint(s)

Five common skeletal manifestations of Gaucher disease will be summarized separately. A single composite endpoint will not be constructed.

1. Mobility, bone crisis and pain: Category of mobility status and bone pain, as well as number of new bone crises, will be summarized. Additionally shifts in category of mobility and pain from study and eliglustat baseline will be presented.
2. Bone marrow infiltration: Bone marrow infiltration score will be summarized both continuously and categorically. Reported values and changes from study and eliglustat baseline will be summarized as data is available.

Category of infiltration score will be constructed and summarized:

Mild: 0 to 4

Moderate: 5 to 8

Severe: 9-16

Shifts in category from study and eliglustat baseline will be summarized.

1. BMD: Bone mineral density in (g/cm²), as well as T and Z scores, will be summarized by time point as well as absolute and percent changes from study and eliglustat baseline.
2. Lytic lesions, fractures, infarctions and osteonecrosis. Incidence of new or worsening lytic lesions, new or worsening AVN, new or worsening infarctions and new fractures will be summarized at the 2 year and end of study time points. Annual incidence rates may also be calculated and summarized.
3. Bone biomarkers: Levels of P1NP, CTx and MIP 1 β , as well as absolute and percent changes from study or eliglustat baseline will be summarized.

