#### **2.1.3.1.1 Gaucher disease clinical assessments (mobility, bone pain, bone crisis)**

Patients will be asked to rate mobility and bone pain as below:

- Current mobility
  - Unrestricted mobility
  - Walks with difficulty
  - Walks with orthopedic aid
  - Requires wheelchair
  - Bedridden
- Level of bone pain during the last 4 weeks as
  - None
  - Very mild
  - Mild
  - Moderate
  - Severe
  - Extreme

In addition, investigators will report the number of bone crisis since the previous assessment. Bone crisis is defined as pain with acute onset, which requires immobilization of the affected area, narcotics for relief of pain, and may be accompanied by one or more of the following: periosteal elevation, elevated white blood cell count, fever, or debilitation of >3 days. Category of number of bone crisis defined as:

- No bone crisis
- 1 – 2 bone crisis
- >2 bone crisis

Gaucher disease clinical assessments will be performed at screening and then yearly.

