#### **2.1.3.1.2 Bone marrow infiltration**

The assessment of bone marrow infiltration is based on the sum of seven bone marrow burden scores for spine (T1-weighted, T2-weighted, infiltration pattern and fat in basivertebral region) and femur (T1-weighted, T2-weighted, and sites of involvement) assessed by MRI views. BMB scores range from 0 to 16 and will only be calculated for patients who have non-missing values for all seven scores.

The BMB score for this study will be assessed by two readers. The primary readers will read in pairs, blinded to patient, treatment, and time point. If readers differ by a score of one or more, for each of the questions, for the femur subtotal, for the spine subtotal and for the overall score, a third reader will serve as the adjudicator and will provide a third read. The average of the three reader results will be used in the analysis. Bone marrow infiltration will be measured at screening and then yearly.

Bone MRI will be read locally and centrally. The central reads will be used for analysis.

Lumbar Spine:

T1-weighted:

0 = Slightly hyperintense  
1 = Isointense  
2 = Slightly hypointense  
3 = Hypointense  
NA = Not assessable

T2-weighted:

0 = Isointense  
1 = Slightly hypointense  
1 = Slightly hyperintense  
2 = Hypointense  
2 = Hyperintense  
NA = Not assessable

Infiltration Pattern:

0 = None  
1 = Patchy  
2 = Diffuse

Fat in basivertebral vein region

0 = Preservation of fat  
1 = Absence of fat  
NA = Not assessable

Femur:

T1-weighted:

0 = Slightly hyperintense or isointense  
1 = Slightly hypointense  
2 = Hypointense  
NA = Not assessable

T2-weighted:

0 = Isointense  
1 = Slightly hypointense  
1 = Slightly hyperintense  
2 = Hypointense  
2 = Hyperintense  
3 = Mixed type  
NA = Not assessable

Sites of Involvement:

0 = No site involvement  
1 = Diaphysis  
2 = Proximal epiphysis / apophysis  
3 = Distal epiphysis  
NA = Not assessable

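### Percent change from baseline is planned for T- and Z-scores, where improvement from a negative baseline comes out negative, and for crisis counts and infiltration scores that can be 0 at baseline

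*SAP*

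**What the plan says.** Both documents plan percent change for T- and Z-scores against two baselines, study entry and first eliglustat dose. SAP 2.4.4.1.3 tabulates it by location and visit and adds "mean plots of absolute values and percent change from baseline for total BMD, T-scores, and Z-scores", with standard deviations. The BMD item of Protocol 11.4.2.1 reads "T and Z scores, will be summarized by time point as well as absolute and percent changes from study and eliglustat baseline".

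The SAP extends percent change to two further components of the primary endpoint:

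- **Bone crises (SAP 2.4.4.1.1):** "Absolute value, change from baseline and percent change from baseline of bone crisis over time will be summarized".
- **Bone marrow infiltration, total and by location (SAP 2.4.4.1.2):** "Absolute values, change and percent change from baseline (study baseline and eliglustat baseline) will be summarized by visit".

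The Protocol names no percent change for either. For crises it plans the number of new ones. For infiltration it says "Reported values and changes from study and eliglustat baseline will be summarized as data is available". SAP 1.5 nevertheless lists no modification to the Protocol's statistical section.

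Neither document gives a percent-change formula or says what happens when the baseline is zero or negative. The only general rule, in SAP 2.4.4, is "Calculations and summaries will include all non-missing data at a given time point, imputation will not be performed".

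**The concern.** Percent change needs a scale with a true zero and baselines well away from it. T- and Z-scores have neither: zero is a reference mean, and patients fall on both sides of it. For a patient below zero, improvement gives a negative percent and worsening a positive one. For a patient above zero the signs are the other way round. A mean over both kinds of patient has no clear reading, and a few baselines close to zero can dominate it.

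Crisis counts and infiltration scores do have a true zero, but zero is also an attainable baseline. Percent change is then undefined, and without imputation the patient drops out of that row. These are the patients who can only stay the same or get worse, so a first crisis in someone with none at baseline cannot appear there.

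Because the study plans no hypothesis tests, the descriptive tables and plots are its result. A percent-change plot that falls beside an absolute-value plot that rises invites misreading of a primary-endpoint component.

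**Working it through.** **Formula.** The SAP states none, so the usual one is assumed: percent change = 100 × (follow-up − baseline) / baseline.

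**One patient.**

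- -1.0 to -0.8 (improved): 0.2 / -1.0 = -20%.
- -1.63 to -2.38 (worsened by 0.75): -0.75 / -1.63 = +46%.
- The same gain of 0.75 gives 0.75 / 0.5 = +150% from +0.5, and 0.75 / -0.05 = -1500% from -0.05.

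**The Protocol's own lumbar spine means (section 4).** These are ratios of group means, not the per-patient percents the SAP plans, but they show the sign.

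| Study and score | Baseline | Follow-up | Absolute change | Percent change |
|---|---|---|---|---|
| Phase 2, T, 4 years | -1.63 | -0.88 | +0.75 | -46% |
| Phase 2, Z, 4 years | -1.17 | -0.48 | +0.69 | -59% |
| GZGD02507, T, 18 months | -1.06 | -0.91 | +0.15 | -14% |
| GZGD02507, Z, 30 months | -1.208 | -0.761 | +0.447 | -37% |

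Every row is an improvement and every percent is negative. The GZGD02507 rows are not fully paired: n falls from 17 to 15 for T and from 38 to 31 for Z. Over the same four years, Phase 2 spine BMD in g/cm² rose 9.9%, a percent change that is sound.

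**How close to zero patients enter this study.** They enter already treated, so the relevant values are the six on-treatment T/Z means and SDs in section 4: (-0.88, 1.26), (-0.48, 1.07), (-0.91, 0.88), (-0.949, 1.1447), (-0.761, 1.076) and (-0.478, 0.787). Under a normal approximation, between 4.8 and 10.5 of 32 baselines would be positive and between 3.2 and 5.4 would lie within 0.2 of zero.

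**Illustrative simulation.** Assumptions: n = 32; normal baselines from those six values; normal change, independent of baseline, with SD 0.15, 0.3 or 0.6; scores rounded to 0.1 or 0.01; exact-zero baselines excluded; 20,000 samples per setting. The range is over the six baselines and three SDs.

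| True mean gain | Samples with negative mean percent change, rounding 0.1 | Rounding 0.01 |
|---|---|---|
| +0.15 | 57–88% | 54–74% |
| +0.05 | 53–70% | 51–63% |
| 0 | about 50% | about 50% |

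For the 4.5-year Z value (-0.478, SD 0.787), a gain of +0.15 and an SD of change of 0.3, the 95% range of the mean percent change is:

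| Denominator | Rounding 0.1 | Rounding 0.01 |
|---|---|---|
| Baseline | -55% to +34% | -163% to +143% |
| Absolute baseline | -1% to +84% | -39% to +244% |

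The absolute-value denominator repairs the sign but not the instability.

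**Zero baselines.** SAP 2.1.3.1.2 states that "BMB scores range from 0 to 16". Under "Category of number of bone crisis defined as", SAP 2.1.3.1.1 lists having no crisis as a category of its own. From a baseline of 0, both 0 to 0 and 0 to any positive value divide by zero. The documents give no frequency of zero baselines, so no size is attached to this part.

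**The case against.** The strongest case against concerns weight and scope.

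- **Valid summaries sit alongside.** Absolute values, absolute changes, category shifts and new-crisis counts are all planned, and there is no test to corrupt. This stands, and it limits the harm to misleading output.
- **The median is steadier than the mean.** Protocol 11.4 plans the median. In the 4.5-year Z setting above, with the usual formula, its 95% range is only about -30% to +10%. That stands against the instability figures, but the median is still mostly negative for a true gain, and the planned plots show means.
- **The T/Z figures come from two studies.** Patients may also enter from GZGD02607, where scores were maintained in the normal range, or from GZGD03109, and the mix is not given. So larger gains against eliglustat baseline are documented only for Phase 2 and GZGD02507 patients. Stable patients suffer less from the wrong sign, but they remain exposed to baselines near zero.
- **Crisis counts and infiltration scores have a true zero.** Percent change is interpretable at any non-zero baseline, and a zero-baseline rule would make the rows well defined. Such a rule would still leave out the patients who cannot improve, and the Protocol does not ask for these rows.
- **The simulation rests on assumptions.** It does. The sign reversal needs none of them beyond the usual formula.

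**Conclusion.** The concern holds. Under the usual formula, the planned T/Z percent-change tables and plots can point the opposite way to the absolute-value plots beside them. The Protocol's own gains become -46%, -59% and -37%. The wrong sign matters most against eliglustat baseline for patients whose scores rose on treatment. Against study baseline, where Protocol 9.5.1 expects stability, the main problem is an erratic mean. The ranges given for that instability depend on the assumed gain, SD of change, rounding, normality and independence of change from baseline.

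For crisis counts and infiltration scores the defect is the silent loss of zero-baseline patients, of unknown number. Percent change in BMD in g/cm² is not in question. The outputs should be corrected, but the study's validity is not at risk.

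**What to change.** - **SAP 2.4.4.1.3:** limit percent change to BMD in g/cm², which is the example SAP 2.4.4 and Protocol 11.4 already use. Replace the T- and Z-score percent-change plots with plots of absolute change.
- **SAP 2.4.4.1.1 and 2.4.4.1.2:** delete percent change for crisis counts and for infiltration scores, total and by location. Rely on the absolute changes and new-crisis counts already planned, and add n (%) by the crisis categories defined in SAP 2.1.3.1.1.
- **Protocol 11.4.2.1, BMD item:** make the same restriction. A Protocol change needs ethics committee approval under Protocol section 15. If an amendment is not wanted for this alone, record the departure in SAP 1.5.

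The cost is wording in three SAP subsections plus one Protocol item or one SAP 1.5 entry. Several percent-change outputs go, the absolute-change plots and a small crisis-category table come in, and no new data are needed.
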